10. SAFETY

Safety analyses will be based on the SAF and summarized across all study periods by Baseline Medication Group. In addition, data from the DBRW will be summarized by treatment group using the DBRW SAF. No inferential statistical analysis will be performed; only descriptive summaries will be provided.

10.1. Exposure

10.1.1. Extent of Exposure

The below exposure information will be summarized based on the SAF using descriptive statistics as well as counts and percentages, as appropriate, depending on the study period. Exposure summaries are based on data collected by the study drug administration eCRF.

- **Across all periods overall and by Baseline Medication Group:** average of total nightly dose of JZP-258 (in g/night), duration of exposure to single doses of JZP-258 > 4.5g, duration of study drug exposure in days, and duration of exposure to JZP-258 in days (excludes time subjects received Placebo in DBRW);
- **Across all periods by Stable Dose Regimen (once nightly vs twice nightly):** starting dose regimen of JZP-258 in OTTP (once, twice, or thrice nightly), time to get to total nightly stable dose (in days), average of total nightly dose of JZP-258 (in g/night), and duration of exposure to JZP-258 (in days);
- **OTTP overall and by Baseline Medication Group:** total nightly starting dose of JZP-258 (in g/night), average of total nightly dose of JZP-258 (in g/night), starting dose regimen of JZP-258 (once, twice, or thrice nightly), number of dose adjustments, time to get to total nightly stable dose (in days), and duration of exposure (in days) regardless of the JZP-258 total nightly received dose;
- **SDP overall and by Baseline Medication Group:** average of total nightly dose of JZP-258 (in g/night) and duration of exposure (in days) regardless of the JZP-258 total nightly received dose;
- **DBRW overall and by Baseline Medication Group:** JZP-258 total nightly received dose (in g/night), and duration of study drug exposure (in days) regardless of the study drug total nightly received dose;
- **SDP and DBRW by Randomized Treatment group:** JZP-258 total nightly received dose (in g/night), duration of exposure (in days) regardless of the JZP-258 total nightly received dose in SDP, and duration of study drug exposure (in days) regardless of the study drug total nightly received dose in DBRW;
- **OLE overall and by Baseline Medication Group:** average of total nightly dose of JZP-258 (in g/night) and duration of exposure (in days) regardless of the JZP-258 total nightly received dose

Exposure summaries reflect all dose changes entered on the study drug administration eCRF. Data from the dosing diary and compliance are not considered for duration of exposure.

Listings of study drug exposure and of the dosing diary will be presented.

10.1.2. Treatment Compliance

Summary statistics for compliance to study drug will be presented using descriptive statistics based on the SAF overall and by Baseline Medication Group or randomized treatment group, as appropriate, across all study periods and by study period. Compliance will also be summarized by category (<75%, 75-125% and >125%) for each period. A listing of compliance will also be presented.

Compliance will be calculated as the volume of solution taken during a study period (i.e. total dispensed – total returned) divided by the volume of solution that should have been taken by the subject during that study period, expressed as a percentage i.e.

$$\text{Compliance (\%)} = \frac{\text{Volume of solution taken during a study period}}{\text{Volume of solution that should have been taken during the study period}} \times 100\%$$

where:

- Volume of solution taken is defined as follows:
Volume of solution dispensed at the end of the previous study period – volume solution returned at the end of the current study period
- Volume of solution that should have been taken during a study period is defined as follows:
{Duration of treatment during the study period i.e., [(Date of the last dose during the Study Period – Date of the first dose during the Study Period) + 1] x volume of study drug corresponding to the subject's assigned dose during the period (refer to Table 4)}

Compliance will not be calculated for the study period if 1 or more dispensed bottles are not returned. No imputation is performed for the volume returned for missing bottles.

Table 4: Total Daily Volume of Solution (mL)

Assigned or Stable Dose of Study Drug (g)	Volume of Solution (mL)
4.5	9
5.0	10
5.5	11
6.0	12
6.5	13
7.0	14
7.5	15
8.0	16
8.5	17
9.0	18

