APPENDIX 3. DOSING DIARY

Study Drug Dosing Diary

To be completed in the morning

Subject Number: _____

Date: _____

How many times did you take your study drug last night?

- 0
- 1
- 2
- 3

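### The compliance denominator runs from first to last dose, so on its plain reading nights left undosed at either end of a period are not counted as missed

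*SAP*

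**What the plan says.** SAP 10.1.2 (Treatment Compliance) takes the solution used up, as dispensed minus returned volume, and has it "divided by the volume of solution that should have been taken by the subject during that study period". That names a whole-period denominator. The operational definition that follows is narrower. It takes "Date of the last dose during the Study Period – Date of the first dose during the Study Period) + 1" and multiplies this by the "volume of study drug corresponding to the subject's assigned dose during the period (refer to Table 4").

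Two further rules matter here. Results are banded: "Compliance will also be summarized by category (<75%, 75-125% and >125%) for each period". There is also one exclusion: "Compliance will not be calculated for the study period if 1 or more dispensed bottles are not returned".

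Nothing elsewhere adds back the missing nights. Protocol 5.8 says that compliance is calculated at visits where drug is returned, but gives no denominator. The dosing diary (Protocol Appendix 3) asks each morning "How many times did you take your study drug last night", so it would show undosed nights. The compliance formula does not use it, however. SAP 10.1.1 says of exposure that "Data from the dosing diary and compliance are not considered for duration of exposure", and plans only a listing of the diary.

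**The concern.** The stated denominator and the calculated one agree only when the subject doses on the first and last nights of the period. Otherwise the calculated one shrinks to the span actually dosed. A night missed between two doses lowers the score, but a night missed before the first dose or after the last one does not. Equal amounts of missed drug can then fall in different bands purely because of timing.

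The case that matters most is a subject who stops taking study drug without formally discontinuing and still attends the end-of-period visit with all bottles. The bottle-return exclusion does not remove this subject, so a value is reported. In the DBRW, what is at stake is whether the compliance table by randomized group describes adherence over the period it is labelled with.

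**Working it through.** **Inputs**
- Strength: 0.5 g/mL (Protocol 5.1).
- Nightly volume: SAP Table 4, 9 mL at 4.5 g up to 18 mL at 9.0 g.
- DBRW length: 2 weeks, taken as 14 nights. Protocol Appendix 1.1 allows the end visit at day 14 to 17.
- Bands: <75%, 75-125%, >125% (SAP 10.1.2).
- Assumptions: the dose dates are those of doses taken; each dosed night uses the full assigned volume; all bottles come back.

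**Reproducing the plan's own figures.** The documents state no compliance result. The only numbers behind the formula are the Table 4 volumes. Volume = dose / 0.5 gives 4.5/0.5 = 9 mL up to 9.0/0.5 = 18 mL, and all ten rows match.

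**Formula.** Let d be the nights dosed, a and b the first and last dosed nights, n the nights in the period, and v the nightly volume.
- SAP rule: d·v / [(b − a + 1)·v] = d / (b − a + 1)
- Whole period: d·v / (n·v) = d / n

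The volume v cancels, so the result is the same at every dose.

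**Worked case.** At 12 mL per night (6 g in Table 4), with the last dose on night 10 of 14:
- Taken: 10 × 12 = 120 mL.
- SAP denominator: 10 × 12 = 120 mL, so 100%.
- Whole-period denominator: 14 × 12 = 168 mL, so 120/168 = 71.4%.

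**By number of nights missed, n = 14**

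| Nights missed | SAP rule, missed at the end | SAP rule, missed mid-period | Over all 14 nights |
|---|---|---|---|
| 1 | 100% | 92.9% | 92.9% |
| 2 | 100% | 85.7% | 85.7% |
| 3 | 100% | 78.6% | 78.6% |
| 4 | 100% | 71.4% | 71.4% |
| 5 | 100% | 64.3% | 64.3% |
| 6 | 100% | 57.1% | 57.1% |
| 7 | 100% | 50.0% | 50.0% |

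Each terminal night missed is worth 1/14, about 7 percentage points. The band changes once (14 − k)/14 is below 0.75, that is, from k = 4. Nights missed before the first dose behave like those missed at the end.

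**Longer interval.** With the visit 17 nights after the End of Stable Dose Visit, stopping after night 12 gives 12/17 = 70.6% and stopping after night 9 gives 9/17 = 52.9%. The SAP rule gives 100% for both.

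**Mixed pattern.** One interior night plus the last five missed gives 8/9 = 88.9% under the SAP rule and 8/14 = 57.1% over the period. The score is exactly 100% only if dosing was complete up to the stop.

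**The case against.** Four points can be made for the plan.

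1. **The date source is open.** SAP 10.1.2 does not say where the last-dose date comes from. The neighbouring exposure summaries use the study drug administration eCRF, not the diary. If that form carries the end of the period as the last-dose date for a subject who stopped silently, the denominator covers the whole period and the problem disappears. This stands as a limit on certainty. Doses taken is the plain reading, but the text does not settle it.

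2. **Ending at the last dose is a recognised convention.** For someone who formally discontinues, compliance while on treatment, read beside duration, is reasonable. This stands for those subjects. It does not cover a subject who remains in the period, because the SAP labels the denominator as the period's volume.

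3. **Other displays may reveal these cases.** A reader might infer that such subjects are invisible. The documents do not support that.
   - SAP 10.1.1 summarises DBRW exposure duration by randomized group, so a true early last dose would appear as a short duration. That would not correct the compliance band.
   - Protocol 5.10 makes a discrepancy of 30 mL or more per bottle a protocol deviation. Four nights leave 4 × 9 = 36 mL to 4 × 18 = 72 mL. Three nights at 9 mL leave 27 mL, below the threshold. Bottle size is not given, nor is it clear whether the expected returned volume counts those nights.
   - SAP 8.6 summarises deviations by baseline medication group across all periods, not by randomized group.

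   These are partial safeguards.

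4. **Nothing inferential depends on it.** The ESS looks back over the past week, so a reader might infer that the primary result is compromised, or that the plan relies on this table to show drug was taken during the look-back. The documents support neither. Compliance sits among the descriptive safety summaries of SAP Section 10. No analysis set in SAP Section 6 is defined by it, and the primary ANCOVA in SAP 9.1.1 does not use it. The compliance condition for randomization in Protocol 4.3.3 is not tied to this formula. This objection stands in full.

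**Conclusion.** The point holds as an inconsistency between a label and its calculation, with a limited reach. On the plain reading, stopping 4 or more nights early in a 14-night DBRW moves a subject from <75% to 75-125%. At 4 nights the reported figure is 100% against 71.4%, and at 7 nights 100% against 50.0%. The same nights missed mid-period are scored correctly.

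This rests on the dose dates being those of doses taken, full dosing up to the stop, the subject remaining in the period, and all bottles being returned. How many subjects meet those conditions cannot be determined from the documents. The consequence is confined to the compliance summaries and listing. The mITT set, the treatment estimate, its p-value and eligibility for randomization are untouched.

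**What to change.** In SAP 10.1.2:
- For subjects who remain in the period, count expected nights from the first scheduled night through the night before the end-of-period visit.
- For subjects who formally discontinue, end the count at the recorded discontinuation date.
- Name the data source for the dates used.

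Optionally, tabulate diary-reported dosed nights by randomized group for the Stable Dose Period and the DBRW. The diary records the number of administrations, not volume, so this would complement the volume-based measure rather than replace it.

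The core change needs only SAP wording and programming. The downside is that reported compliance may be slightly lower.

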10.2. Adverse Events

Adverse events (AEs) occurring from the initial subject ICF signature date until the final study visit will be reported. If the Investigator becomes aware of a serious adverse event (SAE) within 30 days after the last dose of study drug, the event must also be reported. In addition, any SAE assessed as related to study drug or procedure by the Investigator must be reported regardless of time after study termination.

AEs will be coded to system organ class (SOC) and preferred term using the Medical Dictionary for Regulatory Activities (MedDRA), Version 19.1. The investigator will assess the relationship of each AE to study drug. AE with a missing relationship to study drug will be reported as related in the summaries. Severity, as determined by the Investigator, will be classed as mild, moderate, severe, life-threatening or fatal. AE with missing severity will be reported as missing in the summaries.

Note that subjects who acquire COVID-19 or report AEs due to the COVID-19 public health emergency (e.g. anxiety) while on study will be coded accordingly and included in the adverse event summaries.

All AEs will be classified according to the period onset as defined by the following:

- Screening AEs are defined as AEs that started on or after the signature of the initial subject ICF but prior to or on the first dose of OTTP study drug
- Treatment period AEs will be defined as occurring in treatment periods (OTTP, SDP, DBRW, and OLE) based on the onset date and the date of first dosing in each of the treatment periods. AEs that occur on the start of the SDP and DBRW are attributed to the previous period.
- Safety follow-up AEs are defined as occurring after the last dose date until 30 days after the last dose date

A treatment-emergent adverse event (TEAE) is defined as any event with onset date on or after the first dose of study drug, including adverse events that occur until 30 days after the last dose date. For the purpose of calculating treatment emergence, incomplete onset dates will be imputed as detailed in Appendix 2.

Only TEAEs are included in summary tables unless otherwise specified. If a subject has multiple episodes of events coded to the same SOC or PT, then the subject will be counted just once in the summaries for that term. Subject incidence of TEAEs by SOC and PT tables are sorted by SOCs (alphabetical order) and then by PTs (descending order) within each SOC for the overall frequency. For summaries by PT only, PTs will be sorted in descending order of overall frequency.

Each TEAE summary will have two sets of outputs:

- TEAEs by baseline medication group across the entire study (excluding adverse events during the DBRW for those randomized to Placebo) up to 30 days after last dose using the SAF

- TEAEs during the DBRW by randomized treatment group using the DBRW SAF. Adverse events are included as TEAEs up to 30 days after the last dose date or the first dose date in the OLE period, whichever is earlier.

A general overall summary of TEAEs with the number and percent of subjects who experienced the following types of events will be provided:

- Subjects with any TEAE
 - Subjects with any related TEAE
- Subjects with any serious TEAE
- Subjects with TEAE by severity
- Subjects with an AE outcome as death
- Subjects with any TEAE leading to study drug discontinuation
- Any TEAE leading to study drug dose reduction
- Any TEAE leading to study drug dose increase
- Any TEAE leading to study drug dose interruption
- Any TEAE not recovered

Subject incidence of TEAEs tables will be summarized by the following:

- SOC and PT
 - TEAE reported $\geq 2\%$ of by SOC and PT
- PT only
- Maximum severity by SOC and PT
- Treatment-related by SOC and PT
- TEAEs of special interest by category (defined in section 10.2.1) and PT
- TEAEs leading to permanent withdrawal of study drug by SOC and PT

Separate adverse event listings will be provided including the following:

- All adverse events
- Adverse events with an outcome of death
- Adverse events leading to permanent withdrawal of study drug
- Serious adverse events
- Adverse events of special interest, defined in section 10.2.1

Non-TEAEs will be flagged in the listings.

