9.9.3. Safety Analyses

Safety analyses will be performed using the Safety Analysis Set. For the Double-blind Randomized Withdrawal Period, results will be summarized by the actual treatment. Analyses will be descriptive in nature, and no formal statistical testing will be performed.

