11.6. Protocol Adherence – Amendments

The protocol must be read thoroughly and the instructions must be followed exactly.

Any changes in the protocol will require a formal amendment. Such amendments will be agreed upon and approved in writing by the investigator, Jazz Pharmaceuticals, and its designees. The IEC and regulatory authorities (as appropriate) will be notified of all amendments to the protocol. Amendments to the protocol will not be implemented until written IEC approval has been received. Any changes to the planned analyses in the protocol will be documented in the SAP.

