6. ANALYSIS SETS

For the purpose of analysis, the following populations are defined:

Table 2: Analysis Sets

Analysis Set	Description
All Screened	
The all screened analysis set (SCR) will contain all subjects who provided a signed informed consent for this study.
 
This analysis set will be used to summarize the number of screened, screen failure and enrolled subjects.

Analysis Set	Description
Enrolled	
The Enrolled Analysis Set (ENR) will contain all subjects who provided a signed informed consent form (ICF) for this study and were deemed as meeting the inclusion/exclusion criteria of this study by the Investigator and were dispensed study drug.
 
This analysis set will be used to summarize subject disposition, major protocol deviations as classified in the Clinical Trial Management System (CTMS) [the study CRO, IQVIA, manages the CTMS], and inclusion/exclusion from each analysis set.

Safety	
The overall Safety Analysis Set (SAF) will include all subjects who took at least one dose of study medication. The SAF will also be defined for each study period:
 
 • The OTTP SAF will contain all subjects in the ENR who took at least one dose of open label (OL) study drug during the OTTP. Hence, the OTTP SAF will be the same as the overall SAF. • The SDP SAF will contain all subjects in the ENR who took at least one dose of OL study drug during the SDP. • The DBRW SAF will contain all subjects in the ENR who took at least one DB study drug. • The OLE SAF will contain all subjects in the ENR who took at least one dose of OL study drug during the OLE. 
The overall SAF will be used to summarize subjects' demographic and other baseline characteristics data, past medical conditions/diseases, surgical history, medications, IH diagnosis history data as well as exposure to study drug and all safety data; select outputs will also be provided for the DBRW SAF.

Randomized	
The Randomized Analysis set (RND) includes all randomized subjects. Subject disposition for the DBRW will be summarized using this analysis set.

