Modified Intent-to-Treat	
The mITT Analysis Set (mITT) will include all subjects who are randomized to JZP-258 or Placebo, who received at least 1 dose of study drug during the DBRW and have at least one set of post randomization assessments for ESS or IHSS, or a PGIc value at end of DBRW.
 
A set of post randomization assessments is defined as having an end of SDP and end of DBRW value for ESS or IHSS. The mITT includes subjects with any primary or key secondary endpoint data.
 
This analysis set will be used for analyzing efficacy endpoints (primary,

Analysis Set	Description
	secondary, and exploratory). Demographics and other baseline characteristics data, past medical conditions/diseases, surgical history, and IH Diagnosis IH diagnosis history data will also be summarized using this analysis set. For summaries and analyses based on the mITT, subjects will be classified according to randomized treatment group.
PK	The PK Analysis Set will consist of all subjects who received JZP-258 and have any evaluable PK data from at least 1 post dose sample. This analysis set will be used for summarizing the Pharmacokinetic data. Demographic and other baseline characteristics data, as well as exposure to study drug will be summarized.

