7.1. General Methods

Analyses and summary outputs will be generated using SAS® version 9.4 (or higher). Categorical variables will be presented using counts and percentages. Unless otherwise specified, continuous data will be summarized using descriptive statistics comprising of the number of subjects with data to be summarized (n), mean, SD, median, minimum (Min) and maximum (Max).

For quantitative measurements, change from baseline will be calculated as:

- Change from baseline = Test value at visit X – baseline value

Unless otherwise specified, analyses based on mITT or DBRW SAF that intends to compare the two randomized treatment groups or to summarize the data during DBRW will be presented by randomized treatment group. In general, other analyses will be summarized by baseline medication groups. Summaries by baseline medication group (as defined in the electronic database) and baseline medication subgroup of efficacy analyses will be combined if there are too few subjects in any group.

- Group 1 and Group 2 will be combined if there are less than 10 subjects in either group and outputs will be summarized by Group 1 or 2 vs Group 3 vs Group 4.
- If the combined total of Group 1 and Group 2 is less than 10, then Groups 1, 2, and 3 will be combined. In this case, outputs will be summarized by Group 1 or 2 or 3 (Receiving Baseline IH Medication) vs Group 4 (Treatment Naïve).

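### SAP 7.1 and 10.2 group double-blind safety data by randomized arm where the protocol specifies actual treatment, and SAP 7.6 does not list the change

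*SAP*

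**What the plan says.** Protocol 9.9.3, on the safety analyses: "For the Double-blind Randomized Withdrawal Period, results will be summarized by the actual treatment". The Synopsis repeats the sentence. Protocol 11.6 adds: "Any changes to the planned analyses in the protocol will be documented in the SAP".

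The SAP takes a different line:

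- SAP 7.1 sets a default, unless otherwise specified. Outputs on the mITT or DBRW safety set that are meant to compare the two arms "or to summarize the data during DBRW will be presented by randomized treatment group".
- SAP 10.2 defines the double-blind adverse event output as "TEAEs during the DBRW by randomized treatment group using the DBRW SAF".
- SAP 10 is less specific: "data from the DBRW will be summarized by treatment group using the DBRW SAF".
- SAP 6 defines the set by dosing only: "The DBRW SAF will contain all subjects in the ENR who took at least one DB study drug". It gives no rule for assigning these subjects to a column. The only classification sentence in that table is for efficacy: "For summaries and analyses based on the mITT, subjects will be classified according to randomized treatment group".
- The whole-study TEAE output in SAP 10.2 is built by "excluding adverse events during the DBRW for those randomized to Placebo". The 4-week-interval table in SAP 10.2.2 makes the same exclusion.
- SAP 10.1.1, by contrast, computes JZP-258 exposure by taking out the DBRW time in which placebo was received.

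SAP 7.6 lists three differences from the protocol: no interim analysis, the wording about 140 enrolled subjects, and COVID-19 conduct. Safety grouping is not among them.

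**The concern.** A safety table is meant to show what happened to people while they took a given product. The protocol's rule does that. The SAP's rule shows what happened to people assigned to a product, and the two differ only for a subject who was given the wrong one. For that subject the SAP places the double-blind events under a drug that was not taken.

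The exclusions carry the problem beyond the double-blind table. The whole-study and interval tables are meant to describe JZP-258, so they remove events that occurred on placebo. Because the removal depends on assignment, events on JZP-258 in a subject assigned to placebo would also be removed. In the reverse case, events on placebo would be kept as JZP-258 events. SAP 10.2.1 lists special-interest categories such as depressed consciousness and respiratory depression, where a single case can matter to the reader of a table.

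**Working it through.** **Comparison of the text.** The protocol's safety rule is specific and stated twice. Protocol 9.1 says more generally that double-blind results are shown by treatment group, which is compatible with either grouping, so the specific rule in 9.9.3 governs. In the SAP, 7.1 and 10.2 both name the randomized arm, SAP 10 does not say which is meant, and SAP 6 is silent for this set. No SAP section classifies double-blind safety subjects by treatment received.

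**Following one subject through the SAP.** Assume a subject is randomized to placebo, takes JZP-258 throughout the DBRW, and has an event.

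- DBRW TEAE table: the event is counted under placebo.
- Whole-study TEAE table: the event is excluded.
- 4-week-interval table: the event is excluded.
- JZP-258 exposure duration: the time stays in, because on its wording only time on placebo received is taken out.
- Listings: the event appears.

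So the exposure time is kept while the events that fell within it are dropped. For a subject randomized to JZP-258 who took placebo, the event is counted under JZP-258 and kept in the whole-study table, while the time is removed from JZP-258 exposure.

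**Size in the DBRW table.** The documents give no figure on this point to reproduce. The input is 56 per arm (protocol 9.3, SAP 5.4). Let *a* and *b* be the numbers with the event in the JZP-258 and placebo columns by randomized arm, with the misallocated subject included in *b*. Moving that subject to the product received changes the denominators to 57 and 55.

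- JZP-258 column: (a+1)/57 − a/56 = (56 − a)/(56 × 57). At a = 0 this is 56/3192 = 1.75 points. At a = 28 it is 28/3192 = 0.88 points.
- Placebo column: b/56 − (b−1)/55 = (56 − b)/(56 × 55). At b = 1 this is 55/3080 = 1.79 points. At b = 28 it is 28/3080 = 0.91 points.

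**Illustration.** Suppose two subjects who took JZP-258 have an event, one of them randomized to placebo, and nobody who took placebo has it. By product received the table reads 2/57 = 3.5% against 0/55 = 0%. By randomized arm it reads 1/56 = 1.8% against 1/56 = 1.8%, and the difference disappears.

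SAP 10.2 also plans a table of TEAEs at 2% or more and does not say whether the cut-off applies per column or overall. Applied per column, the term qualifies by product received (3.5%) but not by randomized arm (1.8% in each). Applied overall, it is 2/112 = 1.8% either way and nothing changes.

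**Size in the whole-study table.** With about 140 subjects planned (SAP 5.4), one subject is 1/140 = 0.7 points in the overall column, and only if the same term did not also occur in that subject outside the DBRW. In a baseline medication group of size g the shift is 1/g. The documents do not give the group sizes.

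**The case against.** The strongest reply is that nothing in the documents suggests the situation will arise. Randomization and dispensing both run through the IWRS, no misallocation is reported or predicted, and with none the two rules give identical tables. Double-blind safety is also descriptive, so no test or claim depends on it. All of this stands, and it is why the point is minor.

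A second reply is that the SAP may be using the randomized arm as a column label, in contrast to baseline medication group, and not as a deliberate as-randomized rule. There is support for this: SAP 10 and the C-SSRS section say only treatment group, Appendix 1 uses the two terms as output headings, and the explicit classification sentence is confined to the mITT. Loose drafting is the likelier explanation, but it does not remove the conflict. The placebo exclusions in SAP 10.2 and 10.2.2 are conditions for dropping data, not column headings, and they are worded by randomization. The exposure rule in SAP 10.1.1 is worded by receipt.

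A third reply concerns reporting. A reader might infer that events would vanish from the report. The documents do not support that. SAP 10.2 lists all adverse events, with separate listings for serious, fatal, withdrawal and special-interest events, and SAP 8.6 summarizes and lists protocol deviations. What would be wrong is the tabulated attribution.

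**Conclusion.** The point holds as an unlisted contradiction between protocol and SAP, with a conditional effect. If every subject received the assigned product, the effect is zero. For each subject who did not and who had an event, a DBRW column moves by up to about 1.8 percentage points when the event is rare and about 0.9 when it is near 50% incidence. The overall whole-study column moves by about 0.7 at most. These figures assume 56 per arm, about 140 in the safety set, and a subject who took the wrong product throughout the DBRW.

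Two stronger readings are not supported. One is that adverse events have been or will be misattributed in this trial: the documents show no misallocated subject. The other is that each such subject shifts every table by 1.8 points: that is the upper end for rare events in the DBRW table only. Efficacy is not affected, since classifying the mITT by randomized arm is explicit and consistent.

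**What to change.** Change the SAP wording before unblinding:

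- SAP 6: add to the DBRW safety set definition that subjects are classified by treatment actually received.
- SAP 7.1: limit the randomized-arm default to the mITT, and state treatment received for the DBRW safety set.
- SAP 10 and 10.2: name treatment received for the double-blind safety outputs.
- SAP 10.2 and 10.2.2: tie the placebo exclusions to placebo received, so that events and exposure follow the same rule.
- State how a subject who received both products during the DBRW is classified. One workable choice is to count under JZP-258 anyone who took any of it in that period. What matters is that the rule is written before treatment codes are opened.

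If grouping by randomized arm is intended, list it in SAP 7.6 with a reason. If the SAP can no longer be amended, SAP 3 allows the departure to be documented with its rationale in the study report.

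The cost is a few sentences and an as-treated variable in the safety datasets. No new data collection should be needed, assuming that IWRS and drug accountability records identify, once unblinded, which product each bottle contained. If no subject was misallocated, the tables do not change.
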